Appendix G. Health Follow-Up Questionnaire**Mi-Kristal Trial Follow-Up Health Questionnaire**

Instructions: Please answer the following questions to the best of your knowledge. Please record the date the form was completed on the top of this page.

1. Have you been hospitalized since you enrolled in this study?

No
 Yes

6.1 If yes, number of hospitalizations: _____

2. During the past month, how would you rate your sleep quality overall?

Very Good
 Fairly Good
 Fairly Bad
 Very Bad

3. Have you had any falls since you enrolled in this study?

Yes
 No

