1.1.2 Secondary Aim

Secondary aim of this trial include:

Aim 2: To determine whether lactulose therapy improves cognitive function as assessed using the Animal Naming Test (ANT).

2a. Comparison of ANT scores from baseline to 28 days, between the intervention and control arm.

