1.1.3 Exploratory Adverse Event Aims

Aim 5: To determine if lactulose therapy increases the incidence of >5 self-reported bowel movements per day.

5a. Comparison of self-reported episodes of >5 daily bowel movements from baseline to 28 days between the intervention and control arm.

Aim 6: To determine if lactulose therapy reduces the number of self-reported falls.

6a. Comparison of self-reported number of falls from baseline to 28 days between the treatment and control arm.

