1.2 END POINTS

All patients will be followed until death, liver transplantation or final study visit at 28 days post – enrollment.

Primary Endpoint

1. Comparison of SF-8 at 28 days post-baseline, between the two groups.

Secondary Endpoints

1. Comparison of ANT, overall sleep quality, regular daily activity impairment, falls, and average number of daily bowel movements at 28 days, compared between the two groups.

[figure not shown]

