4.3.2 Adherence Assessment

During the 28-day intervention phase, all subjects will be contacted on Study Days 3, 6, 9, 14, 15, 21 and 28 via automated REDCap email or SMS text messages via Twilio service. Study Day 28 will only be collected via REDCap email or phone. These points of contact are to collect data about stool frequency and consistency among all subjects and therefore lactulose adherence in the treatment group. If the subject opts out of Twilio service, the subject can also receive these questions via REDCap automated email or a study coordinator will collect this data from the subject directly via phone or email. On Study Days 3, 6, 9, 14, 21 and 28 subjects will be asked the following questions:

1. "How many bowel movements did you have yesterday? Please respond with a whole number." *If 0-4 bowel movements are reported the subject will exit the survey. If >4, the subject will receive the following instructions:*

Since you had > 4 bowel movements yesterday, please reduce to **one** 20g dose of kristalose (1 packet) packet per day. Please call the study line at [contact] if you continue to have more than 4 bowel movements daily or with any questions or concerns.

On Study Day 15 subjects will be asked:

2. "Please reference the Bristol Stool Chart we provided to you to answer this question. How would you describe your stool looks today? Please respond with the applicable number, between 1-7. *All subjects exit survey after response.*

1. Separate hard lumps
2. Sausage-shaped but lumpy
3. Like a sausage but with cracks on its surface
4. Like a sausage or snake, smooth and soft
5. Soft blobs with clear cut edges
6. Fluffy pieces with ragged edges, a mushy stool
7. Watery, no solid pieces, entirely liquid

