7.4 USE OF TWILIO SERVICE

We will work with the Michigan Institute for Clinical and Health Research (MICHR) to construct our REDCap database and connect it with Twilio. Twilio (<https://www.twilio.com>) is a third-party service used to send automated SMS messages and phone call surveys to users for a variety of purposes. We will use Twilio to send follow-up communications to subjects in the intervention groups on Study Days 3, 9, 9, 14, 21 and 28. The only piece of information transmitted from our REDCap database to Twilio will be the phone number of the participant. Participants will choose to either opt-in or opt-out of using Twilio service. Participants that choose to opt-in to the service must provide informed consent to use the service and must agree to Twilio's privacy policy and terms of service. All participants who refuse to use the Twilio service will be offered alternative means of follow-up including phone, text, and/or email communications directly sent from the study coordinator. No protected health information (PHI) will be requested from the patients or sent by the study team through Twilio. The only information transmitted through Twilio SMS text messages or phone calls will be non-identifiable responses to questions about the number of times per day the subject has bowel movements.

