4.1 If recently removed, how long ago was removal (in months): _____

4.2 If recently removed, specify reason for removal: _____

4. Have you stopped driving within the past 6 months?

 Yes	 Stopped driving more than 6 months ago
 No	

5. Are you dependent upon assistance from anyone for any of the following (check all that apply)?

 Bathing	 Getting out of bed or chair
 Dressing	 Eating
 Using the toilet/going to the bathroom	 None

6. Have you been hospitalized in the past 90 days?

No
 Yes

6.1 If yes, number of hospitalizations: 1 2 3 More than 3

7. Have you had an Emergency Room (ER) visit in the past 90 days?

No
 Yes

7.1 If yes, number of ER visits: 1 2 3 More than 3

8. Do you have ascites (accumulation of fluid in the abdomen)?

Yes
 No
 Unknown

9. Do you currently take diuretics/water pills (e.g. Lasix/Furosemide, Aldactone/Spironolactone)?

Yes
 No
 Unknown

10. Have you had a paracentesis (a procedure to remove fluid from the abdomen) within the last 90 days?

Yes
 No
 Unknown

11. Have you have a Transjugular intrahepatic portosystemic shunt (TIPS)?

Yes
 No
 Unknown

12. Are you currently receiving dialysis?

Yes
 No
 Unknown

13. Do you have diabetes?

Yes
 No
 Unknown

14. Do you have congestive heart failure (CHF)?

- Yes
- No
- Unknown

15. Do you have chronic obstructive pulmonary disease (COPD)?

- Yes
- No
- Unknown

16. During the past month, how would you rate your sleep quality overall?

- Very Good
- Fairly Good
- Fairly Bad
- Very Bad

17. Have you had any falls in the past 4 weeks?

- Yes
- No

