18.1 If yes, number of falls: _____

4. What is the current average number of bowel movements you have per day? _____

5. During the past seven days, how much did your CIRRHOSIS affect your ability to do your regular daily activities, other than work at a job?

By regular activities we mean the usual activities you do, such as work around the house, shopping, childcare, exercising, studying, etc. Think about times you were limited in the amount or kind of activities you could do and times you accomplished less than you would like. If CIRRHOSIS affected your daily activities only a little, choose a low number. Choose a high number if CIRRHOSIS affected your activities a great deal.

CIRRHOSIS had no effect on my work

CIRRHOSIS completely prevented me from working

0 1 2 3 4 5 6 7 8 9 10

CIRCLE A NUMBER

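### Falls are counted once, by undated recall since enrolment, so a lactulose subject who waits for drug reports over a longer, partly untreated window than a control

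*Combined protocol and SAP*

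**What the plan says.** Aim 6 (section 1.1.3, Exploratory Adverse Event Aims) reads "To determine if lactulose therapy reduces the number of self-reported falls". Section 1.2 places falls among the secondary endpoints: "Comparison of ANT, overall sleep quality, regular daily activity impairment, falls, and average number of daily bowel movements at 28 days".

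The only source after baseline is Appendix G item 3: "Have you had any falls since you enrolled in this study", then "If yes, number of falls", with no dates. Section 4.4 collects it at Study Day 28 ± 5. The baseline item in Appendix B is also a recall, but over a fixed period: "Have you had any falls in the past 4 weeks".

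The clock differs by arm. Section 4.2.1 and the footnote to Table 1 set Study Day 1 at randomization for controls and at receipt of Kristalose for the lactulose arm. Section 4.3.1 gives a remotely enrolled subject up to two weeks to collect it.

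On interim contacts, section 4.3.2 says "During the 28-day intervention phase, all subjects will be contacted on Study Days 3, 6, 9, 14, 15, 21 and 28", and its questions concern only bowel movements and stool form. The Summary and section 7.4 instead describe these messages as going to the treatment group. Section 7.4 also limits what they carry: "The only information transmitted through Twilio SMS text messages or phone calls will be non-identifiable responses" about bowel movements.

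Section 6.2 treats every outcome as continuous, compares them by MANOVA and adjusts for baseline covariates by linear regression. It does not mention time at risk.

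**The concern.** The falls question counts from enrolment, while the visit at which it is asked is scheduled from Study Day 1. In controls these start together. In a lactulose subject who waits for drug they do not, so that subject reports falls over more days, and the added days precede the first dose. Because the count is undated, the two periods cannot be separated afterwards. The error sits in one arm and runs against Aim 6. Neither randomization nor baseline adjustment removes it, because the extra exposure arises after randomization.

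A second, softer worry is memory. The Significance section describes early hepatic encephalopathy as reversible change that includes inattention, and Aim 2 hypothesizes better cognition on lactulose. If treated subjects remembered a larger share of their falls, a single recall over a month or more would pull the comparison toward no effect. Baseline recall comes before any such effect, so adjusting for it would not help.

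**Working it through.** **Plan's own figure.** There is none to reproduce. Section 6.1 gives 42 subjects for a quality-of-life effect; no fall rate, effect or power is stated for falls.

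**Inputs from the documents.** Final visit at Study Day 28 ± 5 (4.4); Study Day 1 by arm (4.2.1, Table 1); wait of up to 14 days (4.3.1); about 25 completers per arm (section 2). The true ratios, mean waits, recall shares and fall rates below are assumptions.

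**1. Recall window.** Control: 28 days (23 to 33). Lactulose with wait *d*: 28 + *d*. For *d* = 7 this is 35 days (30 to 40); for *d* = 14 it is 42 days (37 to 47), and 42/28 = 1.5.

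**2. Raw count ratio.** Let falls occur at a constant daily rate in controls and on untreated days, and at *R* times that rate on lactulose. Then

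observed ratio = (*d* + 28*R*)/28 = *R* + *d*/28,

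where *d* is the mean wait across the lactulose arm.

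| Mean wait | R = 1.00 | R = 0.80 | R = 0.70 | R = 0.50 |
|---|---|---|---|---|
| 0 days | 1.00 | 0.80 | 0.70 | 0.50 |
| 7 days | 1.25 | 1.05 | 0.95 | 0.75 |
| 14 days | 1.50 | 1.30 | 1.20 | 1.00 |

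A true 0.70 is fully masked at a mean wait of 28 × 0.30 = 8.4 days. If half the arm waited 14 days and half not at all, the mean is 7 and the 0.95 applies.

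**3. Dividing by the longer window is not enough.** For *R* = 0.70, (14 + 19.6)/42 = 0.80 and (7 + 19.6)/35 = 0.76. The untreated days still dilute the effect, so the count itself must start at Study Day 1.

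**4. Alternative reading of the visit date.** Section 1.2 dates the final visit from enrolment. If that governed, both windows would be 28 days, but part of the lactulose window would still be untreated: ratio = (*d* + (28 − *d*)*R*)/28. For *R* = 0.70 this is (14 + 9.8)/28 = 0.85, or (7 + 14.7)/28 = 0.775. The bias is smaller and in the same direction.

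**5. Recall.** Observed ratio = true ratio × (share recalled on lactulose / share recalled in control). For a true 0.70 with no wait:
- control 0.90, lactulose 0.95: 0.74
- control 0.80, lactulose 0.90: 0.79
- control 0.70, lactulose 0.85: 0.85
- full masking needs a quotient of 1/0.70 = 1.43, for example 0.70 against 1.00
- with the gap reversed (treated subjects report less), 0.70 × 0.90/0.95 = 0.66 and 0.70 × 0.70/0.85 = 0.58

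**6. Power.** Wald test on the log rate ratio, Poisson counts, 25 per arm, two-sided 0.05, true ratio 0.70, complete capture. The variance is 1/(25λ) + 1/(25λ × 0.70). For λ = 0.2, 0.5 or 1.0 falls per control subject, power is about 8%, 13% or 21%.

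**The case against.** A reader might infer something stronger: that by improving cognition lactulose raises the number of falls reported and so conceals its own benefit. The documents do not support that.

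- Better recall raises the share of falls reported; the number still drops if the true reduction is larger, as in the three recall pairs above that favour lactulose.
- No recall accuracy is given, and nothing links a 60-second animal-naming score to remembering falls. The early deficits named are inattention and executive function, not memory.
- Entry is by activity impairment of at least 3 on the WPAI item, without a cognitive test. Disorientation, dementia and treated memory disorder are excluded.
- The trial is open label with no placebo, so treated subjects who expect benefit may report fewer falls. The net direction of reporting bias is unknown.

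These objections stand, and they reduce the recall argument to a possibility. They do not touch the unequal window, which follows from the definitions of Study Day 1 and the wording of the item.

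Against the window argument, two weeks is a ceiling, section 4.3.3 also allows drug to be shipped, and the documents do not say how many subjects enrol remotely or how long they wait. So 1.20 is an extreme, not a forecast. It is also fair that falls are an exploratory aim and that power is poor however they are captured. Finally, interim contacts cannot be assumed for controls: if the Summary and 7.4 govern, a falls question added to those messages would be put to one arm only and would create a new bias.

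**Conclusion.** The point holds for the counting window. As written, the item gives delayed lactulose subjects up to 1.5 times the control window, with the excess untreated, and shifts the raw count ratio upward by *d*/28: 0.25 for a mean wait of 7 days and 0.50 for 14. This assumes a constant fall rate on untreated days, a visit scheduled from Study Day 1, and subjects who take enrolment to mean consent or randomization rather than receipt of drug. The actual waits are unknown.

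Differential recall could add to this or offset it; its size and sign cannot be settled from the documents. The matter is a worthwhile refinement rather than an obstacle. It affects one endpoint, exploratory in 1.1.3 and secondary in 1.2, leaves SF-8 alone, and will not make the falls comparison well powered. In a small trial, though, the falls estimate is useful mainly if it is not biased by construction.

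**What to change.** 1. Reword Appendix G item 3 to ask for falls since Study Day 1, with the calendar date given to the subject. Controls lose nothing, since their Study Day 1 is randomization.
2. State in 6.2 that falls are analysed over the days from Study Day 1 to the final or early-termination visit, for example by a count model with log days as offset. Align section 1.2 with 4.4 on the date from which the visit is counted.
3. Reconcile the Summary and 7.4 with 4.3.2 so that both arms receive the same contacts. Only then add one falls question to the Day 3, 6, 9, 14, 21 and 28 contacts: at Day 3, *how many times have you fallen since [Study Day 1 date]?*; afterwards, *since [date of your last answered message]?* This wording avoids an undefined start at Day 3 and does not lose the interval after a missed reply.
4. Use the reworded Appendix G count where interim replies are missing, and as a cross-check otherwise.
5. Revise the content limit in 7.4 and the consent form.

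Cost: steps 1 and 2 are wording only. Step 3 adds slight burden, some missed replies, and coordinator time for subjects who opt out of Twilio. Counting from Study Day 1 leaves out lactulose-arm falls between randomization and receipt of drug; these should be reported separately, with a stated rule for a subject who never receives it. Shorter recall reduces the memory problem but not open-label expectation.

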18.1 If yes, number of falls: _____

4. What is the current average number of bowel movements you have per day? _____

5. During the past seven days, how much did your CIRRHOSIS affect your ability to do your regular daily activities, other than work at a job?

By regular activities we mean the usual activities you do, such as work around the house, shopping, childcare, exercising, studying, etc. Think about times you were limited in the amount or kind of activities you could do and times you accomplished less than you would like. If CIRRHOSIS affected your daily activities only a little, choose a low number. Choose a high number if CIRRHOSIS affected your activities a great deal.

CIRRHOSIS had no effect on my work

CIRRHOSIS completely prevented me from working

0 1 2 3 4 5 6 7 8 9 10

CIRCLE A NUMBER

Appendix H. Bristol Stool Chart**Mi-Kristal Trial Stool Chart**

Instructions: This Stool Chart (see below) shows pictures of seven different types of stool. In 15 days, we will contact you and ask you to describe what your stool looks like in reference to this chart.

	Type 1 Separate hard lumps
	Type 2 Lumpy and sausage like
	Type 3 A sausage shape with cracks in the surface
	Type 4 Like a smooth, soft sausage or snake
	Type 5 Soft blobs with clear-cut edges
	Type 6 Mushy consistency with ragged edges
	Type 7 Liquid consistency with no solid pieces
